For this cluster randomized trial, we assume a Type I error rate of 0.05 and a desired power of 0.8 for the primary outcomes. Our study will include 60 microclusters (30 intervention, 30 control) with at least 8 participants in each cluster (n=480 across all clusters). We will have no fewer than 480 and can enroll up to 720. The number of participants enrolled will depend on our dynamic enrollment strategy that we've discussed already. We assume an intraclass correlation (ICC) of 0.05. For our primary outcomes (and all survey-based outcomes), we will fit a marginal model using generalized estimating equations (GEE) to estimate the effect of the intervention relative to control. Under these assumptions, we will be able to detect an intervention effect of 0.33 s.d at 80% power with 30microclusters per arm (60 total) and 8 participants per microcluster.⁹ This is a conservative estimate of power since we will adjust for the baseline value of the outcome and other covariates associated with the outcome. If we are only able to sample from 50 microclusters (25 per arm; n=400 across all clusters), we will be able to detect a moderate effect size of 0.37 s.d. at 80% power. Assuming up to 25% attrition between baseline and endline, we would still be able to detect a treatment effect of 0.31 s.d.

Statistical Analysis

Individual-level primary and secondary outcomes

For all primary and secondary outcomes drawn from our two-wave survey of 720 trial participants, we will assess differences in outcomes between the intervention and comparison groups using Generalized Estimating Equation models (GEE) that account for clustering at the study microcluster level. We will use canonical link functions for all outcomes. All models will adjust for the baseline level of the outcome, all microcluster-level characteristics used in the covariate constrained randomization (see randomization protocol),¹⁰ any individual characteristics found to be imbalanced between the intervention and control groups at baseline.

We will conduct an intention-to-treat analysis: participants that move out of (or across) study clusters, separately engage with community partner services while in the control group, or do not engage with these services while in the treatment group will all be considered exposed to their original treatment assignment.

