For secondary outcomes based on microcluster-level administrative data, we will use a difference-in-differences strategy, which leverages additional power from repeat (quarterly) observations that are available in administrative data.¹⁶ Specifically, we will estimate a Poisson-fixed effects model for each secondary outcome on the interaction between binary indicators for calendar time (quarter-year) and binary indicator of intervention status, adjusting for cluster and calendar time (quarter-year) fixed effects (the cluster fixed effect subsumes the main effect for treatment status); microcluster populations at baseline will be used as the exposure terms. This approach is known as an event study specification.¹⁷ The time period of analysis will comprise the 8 quarters prior to intervention and all quarters over the course of the intervention period, which comprises the duration between the end of enrollment and baseline survey data collection to the beginning of follow-up data collection, and the post-intervention period, which all quarters between the beginning and end of follow-up survey data collection. (As data becomes available, we will, in the future, also conduct separate analysis that includes periods 8 quarters after the end of survey data collection, once these data become available. This analysis will be viewed as an extension of our primary difference-in-differences model to assess whether treatment effects were sustained after intervention period ended.)

The coefficients on the terms interacting treatment status with time periods prior to the intervention serve as visual and statistical checks of the parallel trends assumption, which we expect to hold given the randomized

selection of intervention and control groups. However, to address potential failures of the parallel trends assumption, we will conduct a specification test in which we will estimate and trend out of the post-intervention period any differential pre-intervention trends in outcomes between the two groups.¹⁷ The coefficients on the terms interacting treatment status with time periods after the intervention period will recover the overall (dynamic) intervention effect.

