In addition to this "event study specification," we will also estimate a standard difference-in-differences model in which the calendar time $\times \times$ treatment interactions are replaced by intervention period $\times \times$ treatment interaction and a post-intervention period $\times \times$ treatment interaction. These two terms will capture average intervention impacts during intervention implementation and immediately thereafter, with the latter being the treatment effect of interest.

For all models, we will adjust standard errors for clustering at the study microcluster level. We will report both unadjusted and multiple-comparisons adjusted¹⁸ p-values for all outcomes.

Sub-group analyses

For our primary outcomes and survey-derived secondary outcomes, we will estimate the above GEE models separately for the following subgroups:

- Gender (persons identifying as men vs. persons identifying as women; if the sample size permits, we will also consider separate models for trans- and non-binary individuals)
- Level of education (split by the sample median years of schooling)
- Age (over 50 versus under 50)

We will assess statistical differences in treatment effects between categories within each subgroup by estimating versions of our main GEE models that fully interact all terms with the binary subgroup indicator, and assessing the standard error and 95% CI on the interaction between treatment and the subgroup indicator.

Evaluating Mechanisms

In addition to evaluating treatment effects on secondary outcomes, we will assess potential mechanisms underlying intervention effects on the primary outcomes using three *descriptive* (and exploratory) approaches.

First, we will use our survey data to examine the extent to which the non-health secondary outcomes (e.g., food security, financial security, social cohesion, stress, experiences of racism, exposure to crime, engagement with greenspaces, health care utilization) mediate the relationship between the intervention and any impacts on the primary outcomes. Specifically, we will conduct a causal mediation analysis to decompose intervention effects by each set of potential mediators. Our method will follow the strategy of Heckman et al (2013), who use an ordinary least squares based approach.¹⁹

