School performance	Grade point average	Philadelphia School District Data	Continuous	Annual data from 2 years prior to enrollment through 1 year after intervention period complete
Preterm birth	Rate of preterm birth (birth < 37 weeks gestational age)	Pennsylvania birth certificate data	Continuous (rate)	Quarterly data from 8 quarters prior to enrollment and 4 quarters after intervention period complete
Low birth weight	Rate of low birthweight (birthweight < 2000 grams)	Pennsylvania birth certificate data	Continuous (rate)	Quarterly data from 8 quarters prior to enrollment and 4 quarters after intervention period complete
Emergency room utilization	Emergency room visits in the previous 12 months	Children's Hospital of Philadelphia Electronic Health Record	Continuous (rate)	Annual data from 2 years prior to enrollment through 1 year after intervention period complete
Hospitalization	Number of hospitalizations in the previous 12 months	Children's Hospital of Philadelphia Electronic Health Record	Continuous (rate)	Annual data from 2 years prior to enrollment through 1 year after intervention period complete

Qualitative Analysis

We will use an applied thematic analytic approach to qualitative data analysis. Data analysis will coincide with data collection, enabling us to adjust data collection procedures to capture emerging and unexpected phenomena. Starting with the first 3-5 interviews, qualitative data will be coded in cycles by the coding team, led by [name] and performed by the Penn Mixed Methods Research Laboratory. The first cycle of coding will enable generation of a codebook grounded in the data (de novo codes) and in a priori codes reflecting

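### Microcluster outcomes are analysed only by difference-in-differences; estimating the coefficient on the pre-period level would be a cheap precision gain where periods correlate weakly, most plausibly for the birth outcomes

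*Combined protocol and SAP*

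**What the plan says.** Section 9, under the heading on microcluster level secondary outcomes, gives the method and the reason for it: "we will use a difference-in-differences strategy, which leverages additional power from repeat (quarterly) observations that are available in administrative data". The first model is an event study: "we will estimate a Poisson-fixed effects model for each secondary outcome on the interaction between binary indicators for calendar time" (quarter-year) and intervention status, with cluster and calendar effects. The plan notes that "the cluster fixed effect subsumes the main effect for treatment status". Next, "we will also estimate a standard difference-in-differences model in which the calendar time" terms give way to an intervention-period and a post-intervention-period interaction with arm, "with the latter being the treatment effect of interest". A further specification removes any differential pre-trend. No model, main or sensitivity, enters the pre-period level as a covariate.

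The outcomes are crime (Table 1) and six child outcomes (Table 2). Crime, preterm birth and low birth weight are quarterly. School attendance, grade point average, emergency room visits and hospitalisations are listed as "Annual data from 2 years prior to enrollment through 1 year after intervention period complete".

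The survey outcomes are handled differently. Under Statistical Analysis, their models adjust for the baseline value and for the covariates used in the constrained randomisation.

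**The concern.** The post-period interaction in a cluster-fixed-effects model is the pre-to-post change in one arm minus the change in the other, on the log-rate scale for a Poisson model. The pre-period is subtracted in full, however well or badly it predicts the post-period. Where it predicts badly, the subtraction adds noise.

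Differencing protects against fixed differences between groups. Here the clusters were randomised, and the plan itself rests parallel trends on that. The choice can therefore be judged on precision, and in large samples a model that estimates the baseline coefficient is never less precise. What is at stake is wider intervals than the planned data allow, and a greater chance of missing a real effect on the sparsest outcomes, which also face a multiple-comparison adjustment.

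**Working it through.** **No figure to reproduce.** The power section covers the survey outcomes: "we assume a Type I error rate of 0.05 and a desired power of 0.8 for the primary outcomes". It gives no power, detectable effect, rho, event rate or between-cluster variation for any microcluster outcome.

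**Inputs from the documents**
- Clusters: "Our study will include 60 microclusters (30 intervention, 30 control").
- Pre-periods, m: 8 quarters, or 2 years for annual outcomes.
- Post-periods, r, quarterly: the analysis text ties these to the follow-up survey window, dated September 2024 to March 2025 in sections 7 and 8.2. That is 2 full quarters, or 3 counting the partial one. Tables 1 and 2 say 4. All three are shown.
- Post-periods, r, annual: 1.

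**Assumptions.** Equal correlation rho between any two periods in a cluster, and a two-sided 5% level (the plan does not state sidedness).

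**Formulas**, with a common scale factor dropped:
- Difference-in-differences: V_D = (1 − rho)(1/m + 1/r)
- Post-period only, baseline ignored: V_P = (1 + (r − 1)rho)/r
- Baseline-adjusted: V_A = V_P − m·rho²/(1 + (m − 1)rho)
- Power of the adjusted model where difference-in-differences has 80%: Φ(2.802·√(V_D/V_A) − 1.96)

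**Worked cases**
- Quarterly, m = 8, r = 2, rho = 0.05: V_D = 0.95 × 0.625 = 0.594. V_A = 0.525 − 0.02/1.35 = 0.510. Ratio 1.16, power 85.6%.
- Annual, m = 2, r = 1, rho = 0.2: V_D = 0.8 × 1.5 = 1.20. V_A = 1 − 0.08/1.2 = 0.933. Ratio 1.29, power 88.8%.

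Quarterly outcomes, power after adjustment (variance ratio V_D/V_A):

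| rho | 2 post quarters | 3 post quarters | 4 post quarters |
|---|---|---|---|
| 0.05 | 85.6% (1.16) | 87.6% (1.24) | 89.3% (1.31) |
| 0.10 | 84.2% (1.12) | 85.7% (1.17) | 87.0% (1.21) |
| 0.20 | 82.6% (1.07) | 83.6% (1.10) | 84.4% (1.13) |
| 0.50 | 80.9% (1.02) | 81.2% (1.03) | 81.5% (1.04) |

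Annual outcomes: 88.8% at rho 0.2, 85.7% at 0.4, 84.4% at 0.5, 82.3% at 0.7 and 80.7% at 0.9.

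**Against ignoring baseline.** V_D exceeds V_P when rho < 1/(m + 1). That is 1/9 = 0.11 with 8 pre-quarters and 1/3 = 0.33 with 2 pre-years.

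**What rho might be for counts.** With a mean of λ events per cluster-period and between-cluster coefficient of variation k, rho = λk²/(1 + λk²). For λ = 0.70 and k = 0.4, rho = 0.112/1.112 = 0.10. For λ = 0.28 and k = 0.2, rho = 0.0112/1.0112 = 0.01. These λ and k are assumptions. The support for small counts is that each microcluster is built on a 0.125-mile buffer around one block (section 8.2).

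**Simulation check.** Poisson counts with gamma cluster effects, 60 clusters, 1,000 runs per setting. Fixed-effects Poisson was compared with Poisson regression of post counts on arm and log baseline count, with robust standard errors.
- Quarterly (m = 8, r = 4, rate ratio 0.6): power 69% against 80% adjusted at λ = 0.70, k = 0.2; 67% against 74% at λ = 0.70, k = 0.4; 34% against 44% at λ = 0.28, k = 0.2.
- Annual (rate ratio 0.8): 34% against 39% at 5 events a year with k = 0.2; no difference at 60 events with k = 0.4 (implied rho 0.91).
- With no effect, both methods rejected in 4% to 7% of runs.

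A further simulation at 0.25 to 1 events per cluster-quarter with 8 pre-quarters favoured adjustment in every setting, by about 1 to 13 points. No-effect rejection was 4% to 9% across the two methods, so small differences in power should not be over-read.

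**The case against.** The planned analysis is valid. Difference-in-differences is unbiased here, the fixed effects absorb every time-constant cluster characteristic, and these are secondary outcomes. All of that stands: this is a choice between two sound estimators.

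A reader might infer that all the rare and annual outcomes lose appreciable power. The documents do not support that, because they give no rho. Low rho can be argued from small counts for the birth outcomes. No such argument is available for attendance or grade point average, which may be stable from year to year, and at rho of 0.7 or more the gain is under about 2.5 points. Crime, if correlated between quarters, also gains little.

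A reader might also take the plan to claim that difference-in-differences has more power than baseline adjustment. It does not. It credits the extra power to repeated quarterly measurement, which is reasonable as far as it goes. What remains is that this reason does not reach the four annual outcomes and does not explain why differencing was preferred to adjustment.

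Finally, the gain shrinks with fewer post quarters. Under the analysis text's own post-period it may be only 4 to 6 points at rho 0.05 to 0.10. That is correct, and the 2-quarter column shows it.

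**Conclusion.** The point holds as a cheap improvement, not as an error. Planning only cluster-fixed-effects models gives up precision when rho is low. Where difference-in-differences has 80% power, adjustment adds about 4 to 9 points for quarterly outcomes at rho 0.05 to 0.10, and about 6 to 9 points for annual outcomes at rho 0.2 to 0.4. The case is most plausible for preterm birth and low birth weight, conditional for the annual outcomes, and weak for crime and probably for attendance and grade point average.

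The sizes rest on equal correlation between periods and on assumed rho, event rates and between-cluster variation; correlation that decays over time would change them. Nothing here shows bias or an invalid test. Nor does it show that any microcluster outcome is underpowered in absolute terms, since no power is stated for them.

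**What to change.** In section 9, under microcluster level secondary outcomes:

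- Pre-specify for each outcome a baseline-adjusted model of the post-intervention periods: outcome on arm, the cluster's pre-period level, calendar period, city section and the constrained-randomisation covariates, with cluster-level standard errors. This matches how the survey outcomes are already treated.
- Make it the main estimate at least for preterm birth and low birth weight.
- Fix the rule for zero pre-period counts in advance, for example the log of an empirical-Bayes rate with its formula written out.
- Keep the event study and the fixed-effects model to describe dynamics and as sensitivity analyses.
- If a random-intercept Poisson model is considered, present it as an alternative that adds a distributional assumption, not as equivalent.
- Limit the power rationale to repeated quarterly measurement.

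The cost is SAP wording, one extra model per outcome, some degrees of freedom from 60 clusters, and the stated zero-count rule. The calculations above do not include the constrained-randomisation covariates. Because those were balanced by design, their cost should be mainly in degrees of freedom.

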Neighborhood microclusters (hereafter, microcluster) served as the intervention unit for the study. To form these microclusters, a master list of every block, or street segment from one intersection to the next intersection, in the 75 eligible census tracts was created. A total of 8,462 blocks were included in the master list. A shapefile of selected blocks was imported into R. A random block was chosen as an index block and a 0.125 (one eighth) mile diameter buffer was created around that block. All other blocks that fell within this radius were used to form a microcluster of geographically proximal blocks. A block was included in the microcluster if at least half of the street segment fell within the microcluster boundaries. This microcluster formed a study area. All blocks that were included in the microcluster were removed from the master list to ensure no overlap of microclusters. Next, an additional 0.125-mile exclusion zone buffer was created on all sides of each microcluster. The purpose of the exclusion zone was to create an additional buffer between microclusters to minimize potential spillover effects from the interventions. This process was then repeated until 60 total non-overlapping microclusters were in each city section.

Our goal was to have a final set of microclusters that minimized overlap of microcluster exclusion zones to reduce potential spillover and contamination effects across trial arms. To do this in a random manner, the process to create 60 study microclusters with 0.125-miles exclusionary zones was repeated 1,000 times to create 1,000 unique maps. An analysis was run to determine the total area of exclusion zone buffer overlap for each of the 1,000 microcluster map iterations, which was then ordered from lowest to highest. We then selected the bottom microcluster iterations with the lowest exclusion zone overlap. From this list, one iteration was selected at random to determine final study sites.

Randomization

We randomly assigned the 60 microclusters to treatment (intervention, n=30 microclusters) and control (nonintervention, n=30 microclusters) groups. Prior to randomization, microclusters were stratified by city section (West and North). The land area and number of streets in each section was near-equal, allowing for stratification pre-constrained randomization.¹

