Within the city section strata, we conducted a covariate-constrained randomization process in order to ensure balance between microclusters randomized to intervention and those randomized to control based on relevant sociodemographic variables. Covariate-constrained randomization quantifies baseline imbalance of microcluster-level covariates (both categorical and continuous) across all microclusters using a balance metric and then randomly selects one randomization schema from those with acceptable balance. Furthermore, the intraclass correlation coefficient calculation – a measure of reliability – remains unaffected under a constrained randomization model.²

We chose the following covariates to balance on: age (categorized by shares under age 19, 19-49, 50-64, and 65 and above); gender; median income; unemployment rate; amount of vacancy; and tree canopy. We did not balance on race/ethnicity (e.g., % Black) or poverty rates, since initial criteria for study site selection focused on census tracts whose populations were at least 80% Black and with elevated poverty rates. The covariates were measured based on their distribution of means by each microcluster using block group data from the US Census Bureau's 2020 ACS. Each microcluster's mean is the weighted mean for the covariates based on percent of land area in each census block group in which the microcluster sits. A microcluster could be in one census block group or could cross over 2 or 3 census block groups. Following the literature, we used a threshold of 0.2 for standardized mean differences in the covariates.

We used the -cvcrand- package, specifically the -cvrall- function, in R to calculate the final covariate balance metric and selection schema at random after covariate balance by cluster was achieved.²

Enrollment

Participant recruitment will commence in September 2023 and will run through May 2023 (or until we enroll at least 480, but no more than 720, in the main trial). Recruitment in control and intervention microclusters will occur simultaneously. The data analyst who performed the randomization will randomize microcluster order (stratified by intervention and control status and city section) to determine the order in which recruitment occurs.

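### The microcluster difference-in-differences models omit section-specific time effects; if West and North diverge, standard errors for frequent outcomes such as crime are too wide and power is lost

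*Combined protocol and SAP*

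**What the plan says.** Section 8.2 (Randomization) gives the allocation: "We randomly assigned the 60 microclusters to treatment (intervention, n=30 microclusters) and control (nonintervention, n=30 microclusters) groups". City section was the stratification factor, and the constrained draw was made inside each stratum: "Within the city section strata, we conducted a covariate-constrained randomization process". On the size of the sections it says only that "The land area and number of streets in each section was near-equal". It does not give a usable number of microclusters per section, or the split between arms within each.

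Section 9 (Microcluster level secondary outcomes) sets the model: "we will estimate a Poisson-fixed effects model for each secondary outcome", with treatment-by-quarter interactions, "adjusting for cluster and calendar time (quarter-year) fixed effects". A second, standard difference-in-differences model replaces the treatment-by-quarter terms with treatment-by-intervention-period and treatment-by-post-period terms; the post-period term is the main target. On variance: "For all models, we will adjust standard errors for clustering at the study microcluster level". The one trend correction offered is for "any differential pre-intervention trends in outcomes between the two groups", meaning the trial arms.

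No section-by-time term, section-specific trend or stratified re-randomisation test is specified for these outcomes. The adjustment for the constrained-randomisation covariates and the permutation analysis, both also in section 9, belong to the survey GEE models.

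**The concern.** A difference-in-differences model estimates change. Cluster fixed effects remove any constant difference in level between West and North, but not a difference in how the two sections change. When assignment is balanced inside each section, both arms contain the same mix of West and North, so a section divergence falls equally on both arms and largely drops out of the treatment contrast. The cluster-robust variance does not use that information. It sees 60 clusters whose changes fall into two groups and counts the gap between the groups as residual variation between clusters.

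The analysis then gives back precision that the stratification secured. At stake is the chance of missing a real effect on crime, the frequent quarterly outcome. The plan chooses difference-in-differences partly because repeated observations add power, so avoidable loss here works against its own rationale.

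**Working it through.** The plan states no power, standard error or event rate for these outcomes, so there is no figure to reproduce. The check uses a formula and then simulation.

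**Inputs from the documents.** 60 microclusters, 30 v 30; two sections; 8 pre-intervention quarters; Poisson model with cluster effects; standard errors clustered by microcluster.

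**Assumed inputs.** 15 v 15 clusters in each section; 3 post-intervention quarters (follow-up from September 2024 to March 2025 touches three calendar quarters); SD of true cluster change 0.1 on the log scale; m = 10 or 25 events per cluster-quarter; West-North divergence d = 0, 0.1, 0.2 or 0.3 log points (0.2 and 0.3 correspond to about 22% and 35%).

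**Formula.** Let s² be the within-section variance of a cluster's log change, pre to post:

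s² = 0.1² + 1/(8m) + 1/(3m).

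With equal sections, the pooled variance ignoring section is s² + d²/4, while the estimate itself varies only with s². The ratio of the planned standard error to the section-adjusted one is therefore √(1 + d²/(4s²)).

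- m = 10: s² = 0.0100 + 0.0125 + 0.0333 = 0.0558. The SD of the estimate is √(s²/15) = 0.061. Ratios at d = 0.1, 0.2, 0.3: 1.02, 1.09, 1.18.
- m = 25: s² = 0.0100 + 0.0050 + 0.0133 = 0.0283. The SD is 0.043. Ratios: 1.04, 1.16, 1.34.

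**Simulation of the period model** (conditional Poisson, cluster-robust standard error, treatment permuted 15/15 within section). Excess of the planned standard error over the one with section-by-period effects:

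| Divergence | 10 events | 25 events |
|---|---|---|
| 0 | about 1% | about 1% |
| 0.1 | 3% | 6% |
| 0.2 | 10% | 18% |
| 0.3 | 21% | 38% |

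The true SD of the estimate is the same under both models, so the excess is miscalibration rather than real uncertainty. At d = 0.3 the planned model rejects a true null 1.6% (10 events) and 0.8% (25 events) of the time, against a nominal 5%.

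**Power.** Effects of -0.17 log points (10 events) and -0.13 (25 events) give roughly 80% power. By formula, power ≈ Φ(effect/SD − 2 × ratio). At d = 0.3:

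- 10 events: Φ(0.17/0.061 − 2.00) = 78% falls to Φ(0.17/0.061 − 2.37) = 66%, a loss of 12 points.
- 25 events: Φ(0.13/0.0435 − 2.00) = 84% falls to Φ(0.13/0.0435 − 2.68) = 62%, a loss of 22 points.

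Simulation agrees: losses of about 2-3, 6-9 and 12-23 points at d = 0.1, 0.2 and 0.3.

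**Single-quarter event-study coefficients.** With one quarter against one reference quarter, s² = 0.01 + 2/m, which is 0.21 at 10 events and 0.09 at 25. At d = 0.3 the formula gives 1.05 and 1.12. Simulated excess over d = 0.1 to 0.3 is about 1-6% at 10 events and 2-14% at 25.

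**Rare outcomes.** At 1 event per cluster-quarter, s² = 0.01 + 1/8 + 1/3 = 0.468. The ratio at d = 0.3 is √(1 + 0.09/1.873) = 1.02; simulation gives 3% or less.

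**Sensitivity.** Sections of 20 and 40 clusters give nearly the same results. Doubling the SD of cluster change to 0.2 roughly halves the excess at small d and reduces it at large d: at 10 events and d = 0.4 it is 24%, compared with 36% when the SD is 0.1.

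**The case against.** The strongest reply is that the harm depends on something the documents do not show. They give no crime rates, cluster variance or section trends. Site selection points towards similarity: all tracts are in one city, at least 80% Black and above a low-income threshold, and one geographically dissimilar tract was removed. That does not rule out divergence, but nothing makes 0.2 to 0.3 log points the expected case, and at 0.1 the loss is small. This stands, and it is why the point is conditional.

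The reply also holds on reach. A reader might infer that every event-study coefficient and every administrative outcome is materially affected. The calculations do not support that: Poisson noise dominates single-quarter contrasts, and birth outcomes in areas this small are probably too rare to be affected (their counts are an assumption; none are given). The annual school and health-record outcomes were not simulated. A loss of sensitivity in the pre-period checks would need the sections to diverge within the pre-period, which was not tested.

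A reader might also infer invalid inference or false positives. The error runs the other way: with balanced assignment the estimate is essentially unbiased and rejection under the null is at or below nominal. The affected outcomes are secondary; the primary survey analyses use a different model.

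What the reply does not remove is the omission itself. Nothing else in the plan supplies a section-by-time term, and the divergence cannot be known in advance.

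**Conclusion.** The point holds in conditional form. The analysis does not follow the strata used to randomise, and if West and North diverge, the planned standard errors are larger than the true variability of the estimate. It matters mainly for frequent outcomes such as crime, in the standard difference-in-differences model: negligible without divergence, modest at 0.1 log points, and a meaningful loss of power at 0.2 to 0.3. These sizes rest on the assumed event rates, cluster variance, divergence and 15 v 15 split.

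If the split within a section is not 1:1, a small bias is added: an imbalance of one cluster shifts the estimate by about 1/30 of the divergence, or 0.3/30 = 0.01 log points at d = 0.3. This is a free improvement in efficiency and calibration, not a threat to the validity of the trial.

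**What to change.** In section 9 (Microcluster level secondary outcomes), replace the common quarter-year effects with city-section by quarter-year fixed effects in both the event-study and the standard difference-in-differences models, using section by year where the data are annual. Keep the cluster fixed effects and the clustered standard errors. Make the change before the outcome data are examined. It would also help to state in section 8.2 how many microclusters lie in each section and how they were split between arms.

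The cost is a change of SAP wording and one interaction in the code. Section is known for all 60 clusters, so no new data are needed. The model gains one nuisance parameter per period, and its standard error differs by about 1% if the sections do not diverge. In simulation the revised model rejected a true null about 5 to 6.5% of the time, so a small part of the apparent power gain is mild under-coverage.
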